Appendix 3 Listing of Efficacy Parameters and Study Populations Analyzed

Efficacy Parameters	Response Analyzed	Study Populations Analyzed
Primary Endpoints		
PVR	Change from Baseline	ITT, CP
6MWD	Change from Baseline	MITT, CP
Secondary Endpoints		
Clinical Worsening	Proportion	MITT, CP
PVR	Percent Change from Baseline	ITT, , CP
Exploratory Endpoints		
BNP/NT-proBNP	Change from Baseline at Week 22	MITT, CP
WHO/NYHA functional class	Change in numeric scale from Baseline at Week 22	MITT, CP
WHO/NYHA functional class	Proportion of patients in categorical change of WHO/NYHA function class after 22 weeks of treatment.	MITT, CP
Hemodynamic parameters	Change from Baseline at Week 22	MITT
Longitudinal change from baseline in 6 MWD up to 22 weeks		MITT
Longitudinal change from baseline in WHO/NYHA functional class in numeric scale up to 22 weeks		MITT
Time to first event of clinical worsening		MITT

Appendix 4 Multiple Imputation Program Specification and Notes

```
/* imputation is sensitive to sort order of input dataset */
proc sort data=dataset;by group usubjid;run;

/* create 100 imputations noting that they are sensitive to the order of
variables specified in the var statement and the seed (which must be pre-
specified to avoid criticism of data-snooping */
/* note that it is convenient to make ALL vars numeric
Current key:
    group is treatment: Placebo coded to 1
                        APD811 coded to 2
    erastrat is baseline therapy: 'Without ERA' coded to 0
                                'With ERA' coded to 1
    fcstrat: is baseline functional class: 'CLASS II' coded to 1
                                           'CLASS III or CLASS IV' coded
to 2
    walkbase is baseline 6MWD
    probase is log-transformed baseline NT-ProBNP
    worse is clinical worsening event: Event=1; No Event=0
    etio is etiology: 'IPAH'=1; 'OTHER CONDITIONS'=2
    walklocf is 6MWD last observation carried forward
    pvrbase is baseline PVR
    bnpbase is log-transformed baseline BNP
    pvr_ch is PVR change from Baseline to W22 (the dependent variable
of primary interest
)

/* note that the fcs statement allows us to use the logistic model for
binary
Variables and normal distribution for the others */
ods select none;
proc mi data=dataset nimpute=100 out=mi_fcs seed=141662;
class erastrat fcstrat worse group ;
var group erastrat fcstrat walkbase probase worse etio walklocf pvrbase
bnpbase pvr_ch;
fcs logistic(erastrat fcstrat worse group/link=logit) nbiter =100 ;
run;

/* analyse by imputation using the SAP specified model */
/* note that we are also testing the normality of each imputation */
proc sort data=mi_fcs;by _imputation_;run;
proc glm data=mi_fcs;
by _imputation_;
class group fcstraterastrat;
model pvr_ch=group pvrbase fcstrat erastrat /solution clparm;
estimate 'Active - Placebo' group -1 1;
lsmeans group/stderr cl;
ods output ParameterEstimates=mixed_fcs estimates=estimates
lsmeans=lsmeans;
output out = resid r=r;
run;quit;

/* combine results from 100 imputations also picking up variance
information*/
```

```
proc mianalyze data=estimates ;
    by parameter;
    modeleffects estimate;
    stderr stderr;
    ods output ParameterEstimates=est
varianceinfo=varianceinfo(drop=df parm);
run;

ods select all;
proc print data=est; var parameter estimate stderr lclmean uclmean
tvalue probt;
    title 'Multiple Imputation Results';
    format estimate lclmean uclmean tvalue 8.2 stderr 8.3 probt 8.4;
run;
proc print data=varianceinfo label;
title 'Imputation Variance Information';
format betvar winvar totvar 8.3 rivar fracmiss releff 8.4;
run;
/* we want to know how many of the 100 imputations were significantly non-
normal */
ods select none ;
proc univariate data=resid normal ;
    var r;
    by _imputation_;
    ods output testsfornormality=normal_stats(keep=test pvalue);
run;
ods select all;
data wilk;
    set normal_stats(where= (index(Test,'Wilk')));
    if pvalue lt 0.05 then result='Non-Normal';
    else result='Normal';
run;
proc freq data=wilk;
tables result;
title 'Frequency of Non-Normal Imputations';
run;
```

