An analysis of covariance (ANCOVA) model with baseline PVR as a covariate and treatment and baseline WHO/NYHA functional class (II vs, III or IV) and baseline background PAH therapy (With ERA vs. Without ERA) as factors will be used to assess the effect of APD811 on change from baseline in PVR. LSM means for the treatments and the treatment effect and LS Mean difference between treatment will be displayed with 95% CIs and the two-sided p-value will be displayed. The normality of the model residuals will be assessed using Shapiro-Wilks test. Assumptions for the analysis of covariance will be checked, and if not satisfied, parametric analyses will be corroborated with appropriate nonparametric analyses, such as the Wilcoxon rank sum test stratified by baseline WHO/NYHA functional class (II vs, III or IV) and baseline background PAH therapy (With ERA vs. Without ERA). The Hodges-Lehmann estimation of location shift and confidence interval will be produced. If the model residuals is not normally distributed, ANCOVA analysis based on log-transformed data will be performed.

Six minute walking distance (6MWD) will be analyzed using the above ANCOVA method described for PVR, substituting the 6MWD baseline measurement as the covariate. Assumptions for the analysis of covariance will be checked, and if not satisfied, parametric analyses will be corroborated with nonparametric analyses, such as the Wilcoxon rank sum test stratified by baseline WHO/NYHA functional class (II vs, III or IV) and baseline background PAH therapy (With ERA vs. Without ERA). The Hodges-Lehmann estimation of location shift and confidence interval will be produced.

Note that formal testing for secondary and exploratory endpoints will proceed only if the comparison for the change from baseline in PVR is significant. In the event that the treatment effect for PVR is non-significant all subsequent testing of other endpoints will be interpreted only in an exploratory, rather than confirmatory manner.

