4.3.2 Secondary Efficacy Analyses

The percent change from baseline in PVR will be analyzed using the method described for change from baseline in PVR.

In addition, the PVR data (absolute value instead of change from baseline) will be natural log-transformed (\ln) prior to analysis. The dependent variable of the model is the change from baseline for the log-transformed endpoint value (i.e., $\ln(\text{Week 22 value}) - \ln(\text{baseline value})$) or equivalently the log-transformed ratio change from baseline (i.e., $\ln\left(\frac{\text{Week 22 value}}{\text{baseline value}}\right)$). Resultant LS mean estimates will be exponentiated to yield the geometric mean estimates of ratio changes from baseline; resultant LS mean difference estimates from placebo will be exponentiated to derive the geometric mean ratio estimates of ratio changes from baseline that is relative to placebo.

For the proportion of patients who progress to clinical worsening, number (%) of patients progressed in each treatment group and 95% CI will be reported; difference in proportion with 95% CI between treatment groups will be estimated using the method of Miettinen and Nurminen. The effect of APD811 will be compared to placebo using a logistic regression model with model with terms for treatment and baseline WHO/NYHA functional class (II vs. III or IV), and odds ratio and 95% CI will be reported.

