7.4 Handling of Missing Data and Sensitivity Analysis

For the ITT analysis of PVR missing week 22 assessments will be derived using the method of multiple imputation via the SAS/STAT procedure PROC MI and the fully conditional

specification (FCS) method to create 100 imputations resulting in 100 complete datasets. The 100 imputed datasets will then be analyzed using the methods described in Section 4.3.1, with the results of the analyses performed on the 100 datasets combined via PROC MIANALYZE. The imputation model will include the following variables: treatment, baseline PVR, baseline NYHA/WHO functional class category, baseline PAH therapy, baseline values for 6MWD, BNP, NT-proBNP, etiology, last on-treatment 6MWD and whether or not a patient experienced clinical worsening. It is anticipated that the imputation model will converge but should it not do so terms will be removed from the model to achieve convergence. The effects of any such model adjustment will be investigated.

To assess the impact of missing data and robustness of the results, the following sensitivity analyses will be performed for the primary, secondary and selected exploratory endpoints:

- Completers population analyses on primary and secondary efficacy endpoints will be performed without missing data imputation.
- Worst case imputation. For PVR, in all-treated patients, prior to ANCOVA analyses as detailed in Section 4.3.1 missing data at Week 22 due to any reason will be imputed by taking:
 - the worst percentage change from baseline in all patients regardless of treatment group.
 - the baseline observation carried forward.
- An additional 'tipping point analysis' *may* be performed for PVR, post-hoc, in the event that the primary analysis is statistically significant and at least 1 of the worst case imputation analyses yields a non-significant result.

For the proportion of patients who progress to clinical worsening, a sensitivity analysis to assess the impact of missing data will be performed wherein all patients who prematurely discontinue treatment for any reason will be considered to have had a clinical worsening event.

- Imputation of missing or incomplete AE start date
 - If year part of AE start date is missing, then the year of the first treatment date will be assigned.
 - If both month and day part of AE start date are missing, and the year part is the same as year of the first treatment date, then the first treatment date will be assigned;

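### Appendix 4 imputes missing PVR on the raw scale, so a log-scale PVR analysis of the imputed sets meets values with no logarithm and loses precision

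*SAP*

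**What the plan says.** - **Imputation model (SAP Appendix 4).** The imputed variable is defined as "pvr_ch is PVR change from Baseline to W22 (the dependent variable". Raw baseline PVR (`pvrbase`) is a predictor. The comment on the FCS statement gives the logistic model to binary variables, then says "Variables and normal distribution for the others". The PROC MI call has no minimum, transformation or predictive mean matching. The natriuretic peptides are treated differently: "bnpbase is log-transformed baseline BNP", and NT-proBNP likewise.
- **Link to the analysis (SAP 7.4).** "The 100 imputed datasets will then be analyzed using the methods described in Section 4.3.1, with the results" pooled by PROC MIANALYZE.
- **Conditional log analysis (SAP 4.3.1).** "If the model residuals is not normally distributed, ANCOVA analysis based on log-transformed data will be performed". Appendix 4 counts the sets that fail Shapiro-Wilk ("we want to know how many of the 100 imputations were significantly" non-normal), but no count is named as the trigger.
- **Unconditional log analysis (SAP 4.3.2).** After percent change ("The percent change from baseline in PVR will be analyzed using the method described for change from baseline in PVR"), the section adds that "the PVR data (absolute value instead of change from baseline) will be natural log-transformed" and models ln(Week 22/baseline). It names no population.
- **Populations.** Appendix 3 gives ITT and completers to PVR change and percent change, and has no row for the ln ratio. SAP 4.2 makes MITT the default for efficacy variables other than the primary PVR change. SAP Section 9 says that, for PVR, MITT is in effect a completers population.

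**The concern.** Nothing in Appendix 4 keeps baseline plus imputed change above zero. On the raw scale this does little harm, because the primary ANCOVA uses the scale on which the values were drawn. On the log scale a non-positive PVR is undefined, and a small positive one gives an extreme log ratio. By default the undefined record becomes missing and that patient leaves that imputed set. A programmer might instead floor or redraw the value. The SAP chooses none of these.

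There is also a scale mismatch. Raw-scale noise of equal size is a much larger disturbance on the log scale for a patient with low baseline PVR. Both effects inflate the between-imputation variance of the log analysis. At stake are the precision of a supporting analysis and an unspecified data-handling choice.

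**Working it through.** **1. The plan's own figure.** Inputs from SAP 7.1: difference 350, SD 320.3, 28 vs 14 evaluable, two-sided 0.05.
- SE = 320.3 × √(1/28 + 1/14) = 104.8, and 350/104.8 = 3.34.
- Normal power = Φ(3.34 − 1.96) = 0.916; exact two-sample t gives 0.903. The stated 90% reproduces.
- Inflation for 30% dropout: 28/0.7 = 40 and 14/0.7 = 20, as stated. Up to 18 of 60 PVRs could then be missing.

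**2. Tail probability.** With change normal, mean Δ and SD 320.3, P(Week 22 PVR ≤ 0) = Φ(−(B + Δ)/320.3) at baseline B. Protocol 4.2 requires B above 240. The two values of Δ are illustrative. An imputation model that explains part of the variance would have a smaller residual SD.

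| Baseline B | Δ = −200 | Δ = −350 |
|---|---|---|
| 500 | 17% | 32% |
| 600 | 11% | 22% |
| 800 | 3% | 8% |
| 1000 | 0.6% | 2% |

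**3. Simulation.** The documents give neither the baseline distribution nor the form of the change, so both are assumed.
- *Design:* 40 vs 20 patients, 19 scenarios, 1500 trials each, 100 imputations by Bayesian normal regression on the Appendix 4 covariates, missing completely at random, Rubin pooling with small-sample df.
- *Baseline:* lognormal, CV 0.45, truncated at 240, mean 500 to 1100.
- *Change:* multiplicative (9 scenarios), intermediate (3) or additive normal (7). In the last two families true Week 22 PVR was redrawn to stay above 100.
- *Comparison:* the ln-ratio ANCOVA after Appendix 4 imputation against the same ANCOVA after imputing ln(Week 22/baseline) with ln baseline as predictor. Section 4.3.1 does not say which quantity is logged; the ln ratio is assumed, because a negative change has no log.

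| | Multiplicative | Intermediate | Additive |
|---|---|---|---|
| Imputed PVRs ≤ 0 | 2-14% | 3-5% | 3-8% |
| SE excess, 30% missing | 14-41% | 9-16% | 1-9% |
| Power lost, 30% missing (points) | 4-19 | 7-11 | 1-7 |
| SE excess, 10% missing | 7-20% | 5-8% | 2-5% |
| Power lost, 10% missing (points) | 0.6-7 | 2-4 | 0.2-5 |
| Null rejection at 30% missing, Appendix 4 | 0.7-1.6% | 1.0-2.0% | 1.5-2.5% |
| Null rejection at 30% missing, log imputation | 3.3-4.3% | 3.3-4.5% | 2.9-4.7% |

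Two examples at mean baseline 700 and 30% missing:
- Multiplicative, log SD 0.40: SE 0.181 vs 0.147 (ratio 1.23), power 48.0% vs 65.8%. Repeat runs of 300 trials gave 0.181-0.182 vs 0.149-0.150.
- Additive, SD 320.3: SE 0.197 vs 0.194 (ratio 1.02), power 55.7% vs 59.5%. Repeat runs gave 0.200 vs 0.195-0.196.

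**4. How often an undefined log occurs.** With 6 missing (10%), at least one of the 100 sets held a PVR ≤ 0 in 92-100% of trials (89-100% in a repeat). On average 13-54% of the sets did. With 2 missing it was 50-97% of trials (59-88% in the repeat). In a deliberately low-spread case (log SD 0.25 at baseline, 0.20 at Week 22) it was only 40-54% of trials at 10% missing.

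**5. How often the Section 4.3.1 log ANCOVA would run.** Assume it runs when over half the sets fail Shapiro-Wilk. Under multiplicative change it is triggered in 42-82% of trials at 10% missing and 21-51% at 30%. Under additive change the figures are 3-15% and 1-3%.

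**6. Against dropping the missing patients.** At 30% missing, multiplicative, a complete-case ln ANCOVA had SE 0.136 against 0.149 for log imputation (log SD 0.40), and 0.084 against 0.092 (log SD 0.25).

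**7. Primary analysis.** Null rejection of the raw-change ANCOVA was 2.7-5.3% over all scenarios.

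**The case against.** **The ln-ratio analysis may use no imputed values.** Under the MITT default in SAP 4.2, with no Appendix 3 row for the ln ratio, Section 4.3.2 would in effect be a completers analysis and every log would be defined. A reader might infer that it runs on the 100 sets because it sits beside percent change, which is ITT. That is possible, but the SAP does not say it. This objection stands: the only direct link is to the conditional log ANCOVA in 4.3.1.

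**Other analyses already cover the risk.** For failed assumptions, 4.3.1 also plans a stratified Wilcoxon test with Hodges-Lehmann estimates, which needs no logarithm. Completers analyses without imputation are planned for the primary and secondary endpoints. Under missing completely at random, a complete-case ln ANCOVA is at least as precise as log imputation (step 6). So the gain from the fix is relative to the raw-imputed log analysis only. Data missing at random were not simulated.

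**Missingness may be well below 30%.** Protocol 6.8 asks for a catheterization at early termination, and SAP 4.3.1 counts it. This shrinks the precision loss, but undefined logs remain possible to likely with 2 missing.

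**The power figures depend on the df.** Appendix 4's PROC MIANALYZE call sets no complete-data df. With df as coded, the power gap in one 300-trial run at log SD 0.40 was 17 points rather than 21. The SE ratios do not change.

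**Stronger readings fail.** A reader might infer a threat to the primary result or an inflated type I error. The primary is analysed on the scale on which it is imputed, and the raw-imputed log analysis is conservative. Nor does the SAP say that the log ANCOVA replaces the raw-change test.

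**Conclusion.** The point holds in a limited form. If the log-transformed ANCOVA in 4.3.1 is triggered, the plan as written feeds it imputed PVRs that may have no logarithm, gives no rule for them, and adds avoidable variance. The same is true of the 4.3.2 ln-ratio analysis only if it is an ITT analysis.

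The undefined values are likely with about 6 missing PVRs and possible to likely with 2. The precision loss is material if PVR changes are multiplicative and small if they are additive. These sizes rest on assumed baseline distributions, forms of change and completely random missingness; low spread lowers the frequency.

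The primary raw-change ANCOVA is unaffected, and undefined logs do not touch the Wilcoxon/Hodges-Lehmann or completers analyses. SAP 6.3 treats comparisons beyond the primary hypotheses as supportive or exploratory. This is an inexpensive improvement to consider before unblinding; the trial's main conclusion does not depend on it.

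**What to change.** 1. State in Section 4.3.2 and Appendix 3 which population the ln-ratio analysis uses.
2. For any log-scale PVR analysis on ITT (the 4.3.1 log ANCOVA, and 4.3.2 if it is ITT), add a second PROC MI run with its own pre-specified seed. Replace `pvr_ch` by ln(Week 22 PVR/baseline PVR) and `pvrbase` by ln(baseline PVR). Leave the other variables and the FCS statement unchanged.
3. Keep the Appendix 4 run for the primary raw-change ANCOVA and for percent change.
4. Say in Section 7.4 which run feeds which analysis.

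A lower limit alone would define the logs but leave the scale mismatch: in the multiplicative scenarios at 30% missing, redrawing values at or below 50 removed 35-96% of the SE excess.

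**Cost.** A few lines of SAS and a few sentences in the SAP; no new data or patients. In all 19 scenarios the log run's SE for the log ANCOVA was never larger, and its estimate stayed within 0.005 of the complete-data estimate. Power fell in one scenario only, by 0.4 point, with df as coded.

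**Downsides.** There is one more imputation run, and raw and log analyses rest on different imputed values for the same patient. Percent changes at or below −100% also remain possible. Moving percent change to the log run would alter its power at 30% missing by +0.3 to +7 points (multiplicative), −9 to −13 (intermediate) or −7 to −22 (additive), so it is better left where it is. Log-imputed values should not feed the primary, whose SE then rose by up to 76%.

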# 9.3 Sample Size and Power Calculations

For the APD811 versus placebo comparison, 28 patients in the APD811 group and 14 patients in the placebo group will have 90% power to detect a between-treatment difference of 350 dyn·s· cm-5 in PVR. This calculation was based upon the pooled SD estimate of 320.3 dyn·s·cm-5 for the mean change from baseline in PVR at Week 17 observed in the selexipag phase 2 study. Assuming that up to 30% of patients may drop out of the trial before a post-randomization repeat RHC is performed, 40 patients will be randomized to the APD811 group and 20 patients will be randomized to the placebo group. For 6MWD, 40 patients in APD811 group and 20 patients in the placebo group will have 80% power to detect a

between-treatment difference of 50 meters in 6MWD assuming pooled SD estimate of 65 meters

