# 9.5.2 Statistical Analyses of Efficacy Measurements

## 9.5.2.1 Primary Efficacy Analysis

The primary endpoints are listed below:

- Change from baseline in PVR after 22 weeks of treatment
- Change from baseline in 6 MWD after 22 weeks of treatment.

The primary efficacy hypothesis regarding the superiority of APD811 to placebo will be assessed in a stepwise manner. First, the statistical significance of APD811 versus placebo result will be determined for the change from baseline in PVR at the end of 22 weeks of treatment. If the result is significant (p < 0.05, two-sided), the primary hypothesis will be considered satisfied and this study will be declared positive. Subsequently, the change from baseline in 6MWD will only be tested if the change from baseline in PVR is significant. This testing procedure preserves the overall Type I error rate for testing the primary efficacy hypothesis.

An analysis of covariance (ANCOVA) model with baseline PVR as a covariate and treatment and baseline WHO/NYHA functional class as factors will be used to assess the effect of APD811 on change from baseline in PVR. Missing values will be imputed using the last observation carried forward (LOCF) method. Assumptions for the analysis of covariance will be checked, and if not satisfied, parametric analyses will be corroborated with nonparametric analyses or with appropriate data transformations if necessary (i.e., log transformation).

Six minute walking distance (6MWD) will be analyzed using the above ANCOVA method described for PVR, substituting the relevant baseline measurement as the covariate. Missing values will be imputed with last observation carried forward, except if any patient withdraws early due to death or due to clinical worsening without a 6MWT being measured at a termination visit, a worst value of 0 for 6MWD will be imputed.

Note that testing for secondary and exploratory endpoints will proceed only if the comparison for the change from baseline in PVR is significant.

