7 STATISTICAL TECHNICAL ISSUES

7.1 Planned Statistical Power and Sample Size

For the APD811 versus placebo comparison, 28 patients in the APD811 group and 14 patients in the placebo group will have 90% power to detect a between-treatment difference of 350 dyn·s·cm⁻⁵ in PVR. This calculation was based upon the pooled SD estimate of 320.3 dyn·s·cm⁻⁵ for the mean change from baseline in PVR at Week 17 observed in the selexipag phase 2 study.

Assuming that up to 30% of patients may drop out of the trial before a post-randomization repeat RHC is performed, 40 patients will be randomized to the APD811 group and 20 patients will be randomized to the placebo group. For 6MWD, 40 patients in APD811 group and 20 patients in the placebo group will have 80% power to detect a between-treatment difference of 50 meters in 6MWD assuming pooled SD estimate of 65 meters.

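### The pooled PVR test is run without the complete-data degrees of freedom, so the deciding p-value uses a near-normal reference although the ANCOVA has at most 55 residual degrees of freedom

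*SAP*

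**What the plan says.** SAP 7.4 imputes missing Week 22 PVR 100 times, fits the Section 4.3.1 ANCOVA to each completed dataset, "with the results of the analyses performed on the 100 datasets combined via PROC MIANALYZE". It gives no rule for degrees of freedom.

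Appendix 4 gives the program. PROC GLM regresses PVR change on treatment, baseline PVR, functional class stratum and ERA stratum. The pooling call is "proc mianalyze data=estimates", and the statements under it name one estimate and one standard error. No complete-data df is supplied. The program drops df from the variance output and leaves it out of the printed estimates, so the df used would not be visible.

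The pooled p-value decides the trial. The rule in Protocol 9.5.2.1 opens with "If the result is significant (p < 0.05, two-sided" and goes on to declare the study positive. SAP 4.3.1 keeps that rule and makes formal testing of 6MWD and of the secondary and exploratory endpoints depend on it.

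**The concern.** Rubin's basic df formula is a large-sample one: it reflects the uncertainty due to imputation and assumes that the complete-data analysis has unlimited df. A trial of 60 patients does not. The pooling step cannot work out the residual df from an estimate and a standard error, so unless the df is supplied, the reference distribution is close to normal.

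The less data are missing, the plainer the inconsistency. With every Week 22 PVR observed, a multiple-imputation analysis should return the ANCOVA result. Here it would not: the programmed primary test would use a critical value of 1.960, while the SAP's own ANCOVA on the same patients, as in the completers analysis, would use 2.004.

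At stake are the reference distribution behind the one p-value that declares the study positive, and the width of the reported interval. The reference is best fixed before unblinding, as Appendix 4 already does for the seed. Adding the option after seeing a p-value near 0.05 would look selective.

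**Working it through.** **Inputs.** SAP 7.1: "28 patients in the APD811 group and 14 patients in the placebo group will have 90% power" "to detect a between-treatment difference of 350" dyn·s·cm⁻⁵, with a "pooled SD estimate of 320.3". SAP 7.1: "Assuming that up to 30% of patients may drop out of the trial" before a repeat catheterization. Protocol 9.3: "40 patients will be randomized to the APD811 group" and 20 to placebo, 60 in all. SAP 7.4 and Appendix 4: m = 100 imputations. Appendix 4 model: intercept, treatment, baseline PVR, functional class (2 levels) and ERA (2 levels), so 5 parameters. The fraction of missing information, γ, is not in the documents. It is assumed to run from 0 to 0.35, and is about 0.30 when 30% of PVR values are missing.

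**The plan's own figure.** With 28 and 14 patients, difference 350 and SD 320.3, two-sided 0.05, power is 91.6% by the normal formula and 90.3% by the noncentral t with 40 df. The stated 90% is reproduced. Allowing for dropout, 28/0.7 = 40 and 14/0.7 = 20. Complete-data df is therefore at most 60 - 5 = 55.

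**Formulas.** Write r = γ/(1 - γ) for the relative increase in variance.
- As programmed (Rubin): ν_m = (m - 1)(1 + 1/r)² = 99/γ².
- Small-sample (Barnard-Rubin), complete-data df 55: ν_obs = (56/58) × 55 × (1 - γ) = 53.1(1 - γ), and ν* = 1/(1/ν_m + 1/ν_obs).

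The standard error is the same under both rules, so the ratio of critical values is the ratio of interval widths. Example at γ = 0.30: ν_m = 99/0.09 = 1,100; ν_obs = 53.1 × 0.70 = 37.2; ν* = 36.0; 1.962/2.028 = 0.967.

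| γ | df as programmed | t | df with EDF=55 | t | programmed interval narrower by |
|---|---|---|---|---|---|
| near 0 | effectively infinite | 1.960 | 53.1 | 2.006 | 2.3% |
| 0.10 | 9,900 | 1.960 | 47.6 | 2.011 | 2.5% |
| 0.20 | 2,475 | 1.961 | 41.8 | 2.018 | 2.8% |
| 0.30 | 1,100 | 1.962 | 36.0 | 2.028 | 3.3% |
| 0.35 | 808 | 1.963 | 33.1 | 2.034 | 3.5% |

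γ varies between simulated datasets. Allowing for that, the programmed df is about 900-1,250 at 30% missing, 1,900-2,900 at 20%, and 7,000 or more at 10% or less.

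**No missing data.** No simulation is needed here. A t statistic with 55 df exceeds 1.96 in absolute value with probability 5.51%. A statistic of 2.00 gives p = 0.0455 against the normal and p = 0.0504 against t with 55 df.

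**Type I error with missing data.** Simulated null trials with 100 imputations gave the rejection rates below. Ranges show the spread across runs.

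| Missing PVR | As programmed | With EDF= |
|---|---|---|
| 0% | 5.6% | 5.1% |
| 5% | 5.2% | 4.7% |
| 10% | 5.5% | 4.8-4.9% |
| 15% | 5.2% | 4.6% |
| 20% | 4.8-5.0% | 4.3% |
| 30% | 4.1-4.4% | 3.5-3.7% |

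A separate set of 3,000 trials per rate (60 patients, 2:1, ten predictors in the imputation model, values missing completely at random) gave 5.4%, 5.0% and 3.8% as programmed at 10%, 20% and 30% missing, and 4.6%, 4.4% and 3.3% with the adjusted df. The Monte Carlo standard error there is √(0.05 × 0.95/3000) = 0.4 percentage points, so the small excesses at 5-15% missing should not be read too finely. The rates fall as missingness rises because the wide imputation model makes the pooled standard error conservative in a sample this small.

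**The case against.** The best case for leaving the program alone is that the small-sample rule is not closer to 5% where the design expects to be. The plan allows for up to 30% without a repeat catheterization. In the simulations above, at 20% missing the programmed test rejects 4.8-5.0% and the adjusted test 4.3%; at 30% the figures are 4.1-4.4% and 3.5-3.7%. So a reader who infers from the narrower interval that it covers less than 95%, or that the primary test is generally inflated, goes further than the evidence. What is shown across the whole range is that one interval is narrower than another.

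The effect on the decision is also small. Under the planning difference and SD, the two rules would disagree in about 0.3% of trials with 40 and 20 complete patients, and in about 1.1% taking 28 and 14 as a stand-in for 30% missing. Further, SAP 7.4 prespecifies completers and worst-case ANCOVAs with an ordinary t reference, so with few missing values nearly the right p-value would appear alongside.

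All of this stands, and it limits the point to a minor one. It does not remove it. The sensitivity analyses do not replace the deciding p-value. With little missing data the programmed test contradicts the ANCOVA that the SAP specifies. The adjusted test stays at about 5% or below at every rate examined; the programmed one does not.

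**Conclusion.** The point holds as a minor programming correction. The primary p-value and interval rest on a near-normal reference although at most 55 residual df exist, and nothing in the protocol or SAP corrects this. The interval is 2.3% to about 3.5% narrower than the small-sample interval. Type I error as programmed is slightly above 5% (about 5.2-5.6%) at 0-15% missing and at or below 5% at 20-30% missing.

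Two stronger readings are tempting and are not supported: that the error rate is inflated at the missingness the trial was planned for, and that the omission is likely to change the trial's conclusion. Only a p-value close to 0.05 could be affected.

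This rests on the software's default of infinite complete-data df when `EDF=` is omitted, which is standard behaviour but not stated in the documents; on an assumed γ; on 60 patients in the ITT set; and, for the error rates, on simulated data. With only 50 analysed, the interval would be 2.8% to 4.0% narrower for γ from 0 to 0.30.

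**What to change.** Add `EDF=` to the PROC MIANALYZE statement in Appendix 4, set to the PROC GLM error df: n minus 5, which is 55 if 60 patients are in the ITT set. State the rule in SAP 7.4. Stop dropping df from the variance output and print it with the pooled estimate. Do this before unblinding.

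The cost is one program option and a sentence of text. The downside is a slightly more conservative test if 20-30% of catheterizations are missing: about 4.3% down to 3.5%, instead of about 5.0% down to 4.1%. With nothing missing, the option gives 53.1 df (critical value 2.006) rather than exactly 55 (2.004), a negligible difference.
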